We will also consider alternative tasks to test differential attention to drug cues, particularly if the first sample of 12 subjects does not perform as expected. For example, a drug word Stroop (Marhe et al., 2013) with substitution of nicotine and alcohol stimuli could be an alternative. We are planning to pilot alternatives before the project starts so they will be available.

C4. Resting State Functional Connectivity Analysis: We will use the methods of the [name] Laboratory (Miranda-Dominguez et al., 2014) to analyze the rsMRI scans. We will use an ROI-to-ROI approach to calculate connectivity in the pre-processed data, based on the *a priori* regions previously associated with alcohol effects (**Table 3**). Bivariate correlations between the average (BOLD) signal from these regions provide connectivity estimates. Several sources of spurious variance along with their temporal derivatives are then removed from the data through linear regression (e.g., signal from ventricular regions and signal from the white matter). The magnitude of connectivity changes between AUD, NUD, NAUD and CS groups will be compared utilizing two-tailed t-tests. Finally, the raw p values will be corrected for multiple comparisons and thresholded at a false discovery rate (FDR) correction of $P_{FDR} < 0.05$.

ROI	CM x	CM y	CM z	
R/L ACC-SMA	±3	23	42	Sal
R/L MFG (DLPFC)	±38	18	44	Exec
R/L SFG (DMPFC)	±16	18	55	Exec
R/L PPC	±44	-60	36	Exec
R/L PCC	±3	-30	32	Def
R/L rINS	±32	19	1	Sal
R/L rMFG	±39	46	13	Exec
R/L IFG	±55	30	6	Sal
R/L AMYG	±28	-1	-19	Dal
R/L RS	±10	5	-9	Sal
BS	0	-22	-12	Sal

Table 3: Center of mass (CM) for *a priori* ROIs for planned comparison of multimodal imaging measures (SA1). ACC-SMA: anterior cingulate cortex-supplementary motor area, (r)MFG: (rostral) middle frontal gyrus, SFG: superior frontal gyrus, PPC: posterior parietal cortex including angular gyrus (AG), supramarginal gyrus (SMG) and inferior parietal lobule (IPL), PCC: posterior cingulate cortex. rINS: rostral insular cortex, RS: rostral striatum, IFG: inferior frontal gyrus, AMYG: amygdala, BS: brainstem. Sal: salience, Exec: executive.

C5. Cortical Density (VBM) and White Matter Integrity (DTI): These analyses are described in **C7**.

Hypothesis 1b: Connections within the decision-making network will exhibit both anatomical (DTI and VBM) and functional disruption in NAUD, AUD and NUD groups relative to CS. We predict that alcohol and nicotine use are associated with greater cortical (cingulate and prefrontal cortex) thinning and decreased white matter integrity in superior and inferior longitudinal fasciculi and rostral trans-callosal fibers.

Expected Outcomes and Alternatives: Our hypothesis would be supported by finding reduced FA in the tracts that connect (directly or indirectly) regions between which there is decreased functional connectivity. The combined anatomical/functional connectivity analysis we propose has not been previously used in addicted populations, although a similar approach yielded informative data in schizophrenia (Kubicki et al., 2009; Skudlarski et al., 2010). We will perform regular QA to ensure that the quality of the data is high. This will allow us to make any modifications to our protocol and, if necessary, recruit additional subjects. We will consult regularly

with [name] about anatomical and functional connectivity.

SA 2: Develop a machine learning model that integrates behavioral, task and resting state functional activation, volumetric data and structural connectivity that a) differentiates the four groups and b) predicts treatment outcome at 3 months.

C6. Machine Learning: SVM Approach: The SVM algorithm [LIBSVM, (Chang and Lin, 2011)] calculates a hyper-surface that separates the groups. This process requires selection of a kernel function that describes the projection of the feature vector (e.g., AMR in *a priori* ROIs, **Error! Reference source not found.**, **Table 3**) associated with each individual into multidimensional space (e.g., a simple scalar product for a

linear kernel) and requires selection of parameters characteristic of each kernel and a constant, C, that characterizes the error penalty. Our approach (schematic in **Figure 3**) to a machine learning model (Schoelkopf and Smola, 2001) closely follows the method of Ding et al. (2015). **Feature extraction:** The first step in this analysis is extraction of features from the functional, resting state, volumetric and white matter connectivity datasets that will be used in the Support Vector Machine. We plan an ROI based analysis (e.g., see **Table 3**). This set of regions will be adjusted and expanded after preliminary analysis of functional and anatomical measures that statistically separate the four groups. Specifically, we use the following suitably scaled features: 1) average cortical density in the ROIs extracted from VBM; 2), average FA in white matter tracts connecting the ROIs (from atlas tract-based spatial statistics (TBSS)), 3) rsMRI connectivity correlation matrices between ROIs, 4) regional parametric regressor means and 5) clinical and demographic variables.

C6a. Classification of AUD, NUD, NAUD and CS (SA2a): The method can be extended to multigroup classification [see, e.g., (Hsu and Lin, 2002; Forkert et al., 2015); (Lajnef et al., 2015), albeit with somewhat greater complexity. LIBSVM uses the “one-against-one” method, which essentially approaches the problem as multiple binary classification problems (there are 6 binary classifiers for 4 groups). We will use the same set of features as above, but the rank order of features may differ.

C6b. Three-month outcome (SA2b): For the outcome predictor, cigarettes per day and pack-years will be added as a feature. We cross-validate the model using a bootstrapping procedure (**Figure 3**). We plan on testing a range of kernels such as the linear, polynomial, radial, and sigmoid kernels. The data will be divided into a training set and a test set (70%/30% split, stratified by relapse status). For each kernel type, we will use 10-fold cross-validation within the training set to determine optimal parameters amongst a wide range of

values. The SVM’s with the optimal parameters will then be applied to the test set. This procedure will be simulated 10,000 times, from which an optimal kernel and corresponding parameters will be selected.

C6c. Expected Outcomes and Alternatives:

We will examine the performance of the SVM classifier by calculating sensitivity, specificity and balanced accuracy. Sensitivity = $TP/(TP + FN)$, Specificity = $(TN/(TN+FP))$ and Balanced Accuracy = $(1/2)(TP/(TP+FN) + TN/(TN+FP))$, where TP is true positive, FP is false positive, FN is false negative, and TN is true negative. The model will be especially useful if balanced accuracy reaches ~70%. If accuracy is below this number, we will investigate refinements or alternatives to our model building techniques. If SVM methods still prove intractable, we are currently developing alternative methods including a random forest approach and multivariate distance matrix regression [MDMR (Zapala and Schork, 2012)]. These methods have

$$\begin{aligned}
 1.1 \quad V_p &= \frac{M}{(1+kt)} \quad V_p = \frac{M}{(1+h\theta)} \\
 1.2 \quad V_p &= \frac{M}{(1+kt)(1+h\theta)} \Rightarrow \frac{20}{M} = \frac{1}{(1+kt)(1+h\theta)} \\
 1.3 \quad V'_{uc} &= \frac{V_{uc}}{V_{tot}} = \frac{1}{1 \cdot 12 \cdot 3} \int_0^{12} \int_0^3 \frac{dt d\theta}{(1+kt)(1+h\theta)} = \\
 &= \int_0^{12} \frac{dt}{12(1+kt)} \int_0^3 \frac{d\theta}{3(1+h\theta)} = \frac{A_k}{12} \frac{A_h}{3} = A'_k A'_h
 \end{aligned}$$

Figure 2: Analysis of discounting tasks. V_p is the immediate value of the amount M , available after delay, t or odds against, θ = $(1-p)/p$, where p is the probability of receiving the reward.

V'_{uc} is the fractional volume under the discounting surface.

been used to classify individuals with addiction [(Squeglia et al., 2016), random forest] and ADHD [(Yang et al., 2016), MDMR].

C6d. Interpretation: Alcohol and Smoking Groups: We expect that this method will identify a set of brain regions, their function and their connectivity that will differentiate NAUD and AUD groups from each other, from NUD and from CS. We expect that we will confirm damage to white matter microstructure in long tracts connecting, in particular the PPC (AG, IPL) with frontal regions (DLPFC, VMPFC, ACC). We expect functional abnormalities in the salience circuit. We predict that these neural abnormalities will be more pronounced in alcohol users than nicotine users but that co-addicted individuals will exhibit the highest level of abnormality. **Outcome:** We expect that decreased cortical density, sensitivity to cues and reward characteristics, increased FA, poor functional connectivity and co-addiction to smoking will predict poor outcome in the AUD and NAUD groups. We specifically expect that functional and anatomic deficits in salience and, especially, cognitive control regions will be important predictors of outcome.

C7. Specific Methods: Human MRI Imaging Acquisition: We will use the Human Connectome Project (HCP) Lifespan Protocol using a 3T Siemens Magnetom Prisma scanner and a 32-channel phased array head coil. **fMRI (T₂^{*}-weighted):** Three (2 PDD and 1 DSNBACK) T₂^{*}- weighted echo-planar imaging (EPI) functional runs will be acquired (60 slices, 2 mm thick, TR/TE/α=2000 ms/38 ms/55°, matrix=128 × 128, FOV=220 mm², [name]

PAT mode/Accel factor = GRAPPA/2, 310 volumes per run) with an in-plane pixel size of 2.0 mm² while subjects perform the PDD or the DSNBACK. Each run will be 10.3 minutes long. **rsfMRI**: Identical to fMRI settings with 200 volumes. **High-resolution anatomical (T_1 -weighted [T_{1w}])**: One magnetically prepared rapid acquisition gradient echo (MPRAGE) (208 0.8 mm isovoxels, TR/TE/TI/α = 2400 ms/2.24 ms/1060 ms/8°, FOV=256x240 mm, 2x Parallel Imaging, duration 6.38 min), will be acquired for co-registration with functional images and statistical overlay. **High-resolution anatomical (T_2 -weighted [T_{2w}])**: 208 slices, 0.8 mm isovoxels, TR/TE: 3200 ms/564 ms; variable flip angle; FOV 256x263 mm, 2x Parallel imaging; Futsyion 5.57 min. **HARDI**: Two HARDI scans will be acquired (66 axial slices, 2.2 mm thick, TR/TE/α = 4300 ms/96 ms/90°, FOV= 25.6 cm², PAT mode /Accel factor = GRAPPA/2) consisting of six non-diffusion weighted (B_0) images followed by 32 non-collinear directions at $B_0 = 1000$ s mm⁻² and at $B_0 = 2000$ s mm⁻². Each HARDI scan lasts 4.73 min.

C7a. fMRI Standard Preprocessing: Task-related and resting-state fMRI data will be preprocessed identically. We include only scans with minimal movement (< 3 mm) and free of artifacts (Murphy et al., 2013). Functional images will be realigned for motion corrections, unwarped then co-registered to structural images for each subject and then transformed to Talairach coordinates and then resampled into atlas space with 3 mm isovoxels. Motion correction is applied with the standard 6 parameters and then frame-by frame spatial deviations are assessed with the temporal derivative of the time course. The anatomical volume is then

segmented into gray matter, white matter, and cerebrospinal fluid. Next, we apply a temporal bandpass filter (0.009 Hz < v < 0.08Hz), spatial smoothing (6 mm full width at half maximum (FWHM) Gaussian kernel), regression with the 6 rigid body motion parameters, regression of the whole brain signal and regression of the signal for ventricles and white matter. Opposite phase-encode polarity spin echo images will be used to estimate the B_0 distortion field, which will be applied to each gradient echo frame after accounting for estimated head motion. Gradient nonlinearity distortions will be corrected using scanner-specific field maps. Both corrections are vital for proper registration to structural images. Images will

[figure not shown]

Figure 3: Schematic [after Ding et al. (2015)] of the classification approach proposed for SA2a and b.

be preprocessed using AFNI_16.1.26. The motion censoring technique described recently by Power and colleagues (Power et al., 2012;Power et al., 2014;Power et al., 2015), will greatly reduce the residual effect of head motion on observed time courses.

To enable cortical surface-based analyses, fMRI time courses will be sampled to the cortical surface mesh, using the extent of overlap with the cortical ribbon as a weighting factor to account for partial voluming. Voxels with high variability relative to their local neighborhood will be excluded. The functional EPI images will be despiked (3dDespike), slice time corrected (3dTshift), motion corrected (3dvolreg), aligned to warped MPRAGE (align_epi_anat.py) and corrected for oblique slice acquisition. A 4 mm FWHM three-dimensional Gaussian blur will be applied to the functional images (3dmerge) and each voxel time series will be scaled to have a mean of 100 (3dTstat, 3dcalc). **Anatomical (T_1 w and T_2 w)**: MPRAGE and T_2 w structural images will be corrected for gradient nonlinearity distortions using scanner specific, nonlinear transformations, provided by MRI scanner manufacturers, and verified using phantom scans. Spatial distortion in the readout direction due to B_0 variation will be corrected based on the distortion maps generated from our fast field mapping. T_2 w images will be registered to T_1 w images using mutual information after coarse pre-alignment via within-modality registration to atlas brains. Intensity non-uniformity correction will be performed by dividing image intensities by a smooth bias field estimated from the geometric mean of the T_1 w and T_2 w images. Anatomical scans will be

[name]

Version date: 2-1-2021

corrected for oblique acquisition, skull stripped (3dSkullStrip), and warped into MNI-152 space with @auto_tlrc.

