Hypothesis 1b: **We hypothesize** that connections within the decision making network will exhibit both anatomical (measured by DTI and VBM) and functional disruption in NAUD, AUD and NUD groups relative to CS. We predict that alcohol and nicotine use are associated with greater cortical (cingulate and prefrontal cortex) thinning and decreased white matter integrity in superior and inferior longitudinal fasciculi and rostral trans-callosal fibers.

SA 2: Develop a machine learning model that integrates behavioral, task and resting state functional activation, volumetric data and structural connectivity that a) differentiates the four groups and b) predicts treatment outcome at 3 months.

Hypothesis 2a: **We hypothesize** that a support vector machine (SVM) learning paradigm can exploit the substantial differences in quantitative neuroimaging measures among NAUD, AUD, NUD and CS groups (obtained in **SA1**) to construct and validate a quantitative classifier that predicts group membership. The classifier will produce a neural model that offers insight into the specific neuroadaptations that occur in co-addiction.

Hypothesis 2b: **We hypothesize** that an SVM classifier can be used to predict treatment outcomes and provide intermediate phenotypes that can be used in future treatment studies. We predict that co-addiction to nicotine is an additional risk for alcohol relapse and make a primary prediction that subjects in the NAUD group will be more likely to relapse than AUD only. Secondarily, we expect that subjects who maintain sobriety will show decreases in responsivity to reward characteristics and show recovery from decreased cortical density and fractional anisotropy. We further hypothesize that comparison of imaging measures at baseline and three months will find recovery associated with improved pre-frontal cortical structural and functional integrity.

[name]

Version date: 2-1-2021

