C. Research Design and Methods (Figure 1): The overarching aim of this proposal is to neurobiologically characterize and predict the effect of NAUD co-addiction on the outcome of patients who enroll in alcohol abuse treatment. In order to accomplish this goal, we will recruit four subject groups who will be characterized primarily with anatomical and functional neuroimaging (**SA1**). These measures will yield elements that become part of a quantitative predictive model that characterizes the neurobiological signatures of AUD, NUD, CS and NAUD co-addiction (**SA2**). These subjects will be well characterized with respect to their substance use and will then be evaluated with two functional MRI (fMRI) tasks, resting state MRI (rsMRI), high resolution anatomical MRI, standard DWI and high angular resolution diffusion imaging (HARDI). Imaging data will be used to test specific hypotheses about the effects of alcohol and nicotine on the brain and behavior.

C1. Subject Recruitment and Initial Evaluation:

Two hundred subjects, ages 18 to 55, will be recruited from the Portland VA, Oregon Health & Science University (OHSU), community substance abuse treatment

Group	Inclusion Criteria
CS	If any history of severe addictions to other substances must be at least 5 years clean. No history of gambling. Less than 20 lifetime cigarettes or equivalent.
NUD	DSM-V criteria for Nicotine Use Disorder Current Smoker, at least 5 cigarettes/day. If any history of severe addictions to other substances must be at least 5 years clean. No history of gambling.
NAUD	DSM-V criteria for Nicotine Use Disorder and Alcohol Use Disorder. At least 8 heavy drinking episodes in the past month. Current Smoker. Alcohol free from 2 to 8 weeks. If any history of severe addictions to other substances must be at least 5 years clean. No history of gambling.
AUD	DSM-V criteria for Alcohol Use Disorder. At least 8 heavy drinking episodes in the past month. Alcohol free from 2 to 8 weeks. Less than 20 lifetime cigarettes or equivalent. If any history of severe addictions to other substances must be at least 5 years clean. No history of gambling.

Table 1: Inclusion criteria emphasize both diagnostic (DSM-V) and severity of use criteria for each group.

Clinical Interview^a
- Demographics
- Medical History
- Psychiatric History
- Substance Use History – Timeline Followback
 Tobacco Use (Current and lifetime)
 Alcohol Use (Current and lifetimes)

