Subjects who call in response to advertisements will be given a brief screening interview to verify age, gender, treatment status, time abstinent, current medications, concurrent medical illnesses and contraindications to MRI. Additional questions will be asked to screen for recent exposure and symptoms of COVID-19. If recent exposure or symptoms are disclosed, and the subject otherwise qualifies, we will wait to schedule them until they have self-isolated for two weeks from time of exposure and/or when their symptoms have completely resolved. Our screening criteria already excludes those who are at increased risk of severe [name]

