illness from COVID-19; however some subjects who *might* be at an increased risk may still qualify to participate during modified operations including smokers and those with well-controlled moderate-to-severe asthma, hypertension, and/or high blood pressure. These subjects will be informed that they may be at higher risk for COVID-19 infection and they may not want to put themselves at risk by participating in research. Contact information will be collected on the screening form for scheduling purposes and, if the potential subject agrees, email will be collected to send an appointment confirmation email (Azure). Subjects are excluded for significant medical problems or drugs known to affect functional MRI. Subjects who fall under the AUD or NAUD group will undergo a breathalyzer test before consent and at the beginning of visits 2, 3, and 7. If a subject has a blood alcohol content (BAC) above 0.08 they will be either excluded from the study or have the study visit rescheduled. The breathalyzer test result before consent will not be collected and is intended to ensure subject is fully capable of consenting. Subjects will be screened for COVID-19 symptoms during confirmation calls prior to study visits and again at the beginning of each in-person visit along with a temperature check. If any symptoms are revealed, the visit will be rescheduled for at least two weeks or until symptoms are resolved. Subjects will be evaluated per the Standardized Human Participant Protocol used by the Translational Service Core of the Methamphetamine Abuse Research Center (MARC) (**Table 1**). To maximize the quantification of alcohol and nicotine use, the instruments have been modified to emphasize both recent (30 days prior to sobriety) and lifetime substance use with the National Institute of Drug Abuse PhenX Toolkit and the Alcohol Use Disorder and Associated Disabilities Interview Schedule 5 (AUDADIS-5). The evaluation includes diagnostic instruments, a battery of cognitive tests, standard measures of impulsivity, PDD, the Stop Signal task, DSNBACK and the Barratt Impulsiveness scale. NAUD and AUD subjects will be required (as an inclusion criterion) to permit contact with two reliable collateral informants, preferably family members with whom they have regular contact. Collaterals will be contacted to obtain their consent to be an informant for the study and contacted if subjects drop out. Subjects will also be asked to give permission to contact clinicians (case managers, physicians) involved in their care. The [name] Lab has established relationships with community treatment programs (including alcohol-specific centers) from prior projects which will facilitate our recruitment. Subjects who are veterans will also be asked for permission to look at their VA medical records for recent blood test results, medication and drug use, as well as treatment/relapse status. This information may be used as study data and blood test results may be used in lieu of repeat testing for the study.

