
Subjects will be reimbursed for the initial assessment visit (\$50) and for the MRI visit (\$100) as well as the result of one choice, chosen at random, during the scanner PDD task (average = \$55, this gift card may be given immediately or delayed up to one year and it may range from \$0 - \$140, depending on the random answer selected. During the task, subjects will choose whether they want \$20 now or a different amount at a later date- we will randomly select one of their answers). The third visit for cognitive battery will be an additional (\$50). Subjects who participate in follow ups (NAUD and AUD groups) will receive \$40 for each monthly visit and individuals receiving a second scan will be paid an additional \$100 and variable amount (average \$55, also may be delayed). Additionally, any enrolled subject who refers another individual will receive \$10 for each referral that participates in the first visit of the study. Some of these visits may be combined but reimbursement will remain the same. To avoid giving subjects cash, payment is provided in the form of widely accepted gift cards. **Comments:** As VA subjects are overwhelmingly male, special efforts will be made to recruit women, not only veterans, but from community detox and treatment programs. Gender is an important consideration and will be used as a covariate in all our analyses and gender effects will be specifically investigated in both Aims. We make special efforts to collect severity of use criteria, including age of onset, lifetime use and average daily use. We will use these variables as covariates and explore dependence of imaging measures on severity criteria.

Subjects may be contacted over the phone at two weeks after Visits 3, 4, and 5 so that we maintain contact and reduce drop out. Subjects will be asked to provide information kept in their study journals (see C3b2) including alcohol and cigarette use. If subjects are unable to make it to Visits 4, 5 or 6, these visits may be conducted over the phone and subjects will be paid at their next in-person appointment.

Appointment confirmation emails may be sent. They will be sent to participants using Azure. Brief scheduling correspondence may also happen through Azure if the study team is not able to connect with the subject via phone.

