A clinician will be available to consult with any participants who experience discomfort for any reason during the study visit. Subjects will be asked to remain in laboratory either until the problem has been resolved or immediate referral to appropriate treatment is accomplished. Subjects not in need of emergent treatment will be offered referral to counseling or other support resources as appropriate. Substance-dependent subjects (except control smokers) will all be in remission and undergoing residential treatment to ensure availability of counseling and support after study visits. The subject may request termination of the assessment at any time.

Subjects may refuse any single non-critical procedure in the study if it makes them uncomfortable without disqualification from the rest of the study.

C11. Participation of Non-Veterans: This is an ambitious study and requires recruitment of subjects who have been abstinent less than one month and one group of subjects who have AUD, but do not use nicotine. There are also significant gender effects which necessitate having a gender balanced sample. We will, therefore, need to recruit non-veterans to meet our ambitious recruitment goals, recruit sufficient women and subjects rare in the veteran treatment population. The [name] lab has established relationships with treatment programs within and outside the VA Portland HCS which will facilitate recruitment. Non-veterans will be recruited from community alcohol detox and treatment programs, through advertisement on OHSU's Study Participation Opportunities web page, and, if necessary for controls, Craig's List.

C12. Potential Benefits of Research to Subjects and Others

This project is not intended to benefit individual subjects but results may help us understand the neurobiology of alcohol and tobacco co-addiction and tailor treatment approaches to co-addicted individuals seeking treatment in the future.

C13. Importance of Knowledge to be Gained

The results of this project will be valuable for planning treatment options for dually addicted individuals by [name]

predicting and evaluating treatment response using neuroimaging. A predictive model will help individualize relapse risk through a better understanding of neurobiological factors that influence addiction, craving and cognition.

C14. Data and Safety Monitoring Plans

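### Days since last drink can range from 14 to 56 at entry, yet are not a named covariate in the AUD-versus-NAUD comparisons

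*Combined protocol and SAP*

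**What the plan says.** **Entry.** In C1, Table 1, the AUD row reads: "At least 8 heavy drinking episodes in the past month. Alcohol free from 2 to 8 weeks". The NAUD row carries the same two conditions. Neither row says when the month ends or on which date abstinence is judged. Elsewhere in C1 the interview instruments are said to "emphasize both recent (30 days prior to sobriety) and lifetime substance use". C11, which explains why non-veterans are needed, says the study "requires recruitment of subjects who have been abstinent less than one month".

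**Collection.** The telephone screen in C1 is to "verify age, gender, treatment status, time abstinent, current medications", among other items. Table 2 lists a Timeline Followback, and C3b2 has all subjects keep study journals.

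**Adjustment.** The C1 comments promise gender as a covariate in all analyses. They continue: "We make special efforts to collect severity of use criteria, including age of onset, lifetime use and average daily use". Then: "We will use these variables as covariates and explore dependence of imaging measures on severity criteria". The C2 comments add cannabis and other recreational drug use for statistical control. C4 compares resting-state connectivity between groups with two-tailed t-tests. C6 lists clinical and demographic variables, unspecified, as classifier features, and C6b adds cigarettes per day and pack-years for the three-month outcome. Time abstinent is named in none of these places.

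**Why time sober is relevant in the plan's own terms.** Under Hypothesis 2b, subjects who stay sober are expected to "show recovery from decreased cortical density and fractional anisotropy". The primary prediction there is more relapse in NAUD than in AUD alone.

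**The concern.** The AUD-versus-NAUD contrast is how the study isolates the contribution of nicotine. Two of the measures compared, cortical density and fractional anisotropy, are ones the plan expects to change with sobriety. One subject may be scanned two weeks after the last drink and another eight weeks after. If one group has on average been sober longer, part of an imaging difference could be credited to nicotine when it belongs to time sober.

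The relapse comparison has the same exposure. A subject entering at eight weeks has already passed six weeks that a subject entering at two weeks has still to face.

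The variable is collected, so adjustment is possible. What is missing is a commitment to it. Without one, the decision to adjust can be taken after the results are known.

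**Working it through.** The plan gives no figure on this point to reproduce. The 0.99 power in C8 comes from a pilot AUD-versus-control map without a stated effect size, and it does not bear on the question.

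**1. Range of days sober.** Two to eight weeks is 14 to 56 days, which is 43 possible values.
- If the month ends at sobriety, as C1 has it for the instruments, all 43 values are compatible with eight heavy drinking episodes.
- If a 30-day month ended at assessment, the drinking days left in it would be 30 − d, where d is days sober. At one episode per day, 30 − d ≥ 8 gives d ≤ 22, or 9 of 43 values. With no limit on episodes per day, d ≤ 29, or 16 of 43.
- The C11 wording, less than one month, also covers days 14 to 29, or 16 of 43.

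These are counts of days in the window, not of candidates.

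**2. Size of a possible bias (illustration; every input except 50 per group is assumed).** Let r be the within-group correlation of days sober with an imaging measure, g the difference in group means, and s the within-group SD in days. With no true group effect, the spurious standardised difference is d = r × g / s. I take s = 12.4, the SD of an even spread over 14 to 56 days: √((43² − 1)/12) = 12.41. It serves only as a scale, since two groups each spread evenly over the whole window would have no gap. With 50 per group the noncentrality is d × √(50/2) = 5d on 98 df, two-sided 5%.

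| Gap g (days) | r = 0.1 | r = 0.2 | r = 0.3 |
|---|---|---|---|
| 3.5 | 5.2% | 5.9% | 7.0% |
| 7 | 5.9% | 8.6% | 13.3% |

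For example, 0.3 × 7 / 12.41 = 0.169, and a noncentrality of 0.85 gives 13.3%.

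If the month ended at assessment and days sober were confined to 14 to 22 (SD 2.6), the same per-day slopes with a 2-day gap would give 5.1% to 5.7%. The point therefore matters mainly under the sobriety-anchored reading.

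**3. Price of adjustment.**
- *Degrees of freedom.* At an assumed d of 0.6 and 50 per group, power is 84.4% with 98 df and 84.4% with 97.
- *Standard error.* Adjusted over unadjusted is √(VIF × (1 − r²)), with VIF = 1 + g²/(4s²). For g = 7, VIF = 1 + 49/(4 × 154) = 1.080. The ratio is 1.034, 1.018 and 0.991 for r = 0.1, 0.2 and 0.3, so the change runs from +3% to −1%.

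**The case against.** The case against is substantial, and much of it stands.

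- **No imbalance is shown.** Both alcohol groups have the same window, which limits how far they can differ. A reader might infer a difference from the Specific Aims, where 90% of veterans treated for AUD in the local VA program also have NUD, and from C11, which turns to community programs for subjects rare among veterans. The documents do not carry it that far. Community recruitment also serves to enrol women, and C10 says substance-dependent subjects other than control smokers will all be in residential treatment. Nothing reports days sober by source or by group.
- **The recovery hypothesis is longitudinal.** It compares baseline with three months in subjects who stay sober. It does not state that differences within 14 to 56 days matter at baseline. It makes the variable relevant but does not prove an effect.
- **Adjustment is not excluded.** The severity list is open, and the classifier's clinical variables could include time abstinent. The gap is in naming it.
- **Table 1 does not contradict itself.** A reader might infer that eight episodes in the past month cannot coexist with up to eight weeks alcohol free. That holds only if the month ends at assessment. The one anchor in the documents, the 30 days before sobriety, makes every day fit, though it is attached to the instruments and not to Table 1. The C11 phrase is a recruitment rationale, not an eligibility rule.
- **A classifier feature is not adjustment.** This is correct, and the fix below does not rely on it.

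The objection that C4 specifies t-tests carries less weight. The C1 comments already promise gender as a covariate in all analyses, and a plain t-test cannot include one.

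**Conclusion.** The point holds as a cheap improvement to the analysis plan. It does not show a bias. A variable that can range fourfold at entry, that the plan's own recovery hypothesis makes relevant, and that is already collected should be a named covariate in the AUD-versus-NAUD comparisons.

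The direction and size of any bias are unknown. The range of 5.2% to 13.3% rests on assumed gaps, correlations and spread. Its upper end needs both a 7-day gap and a correlation of 0.3. The documents do not support the statement that the planned contrast is confounded.

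The differing descriptions of the look-back month and the abstinence period need reconciling, but that is a matter of wording.

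**What to change.** 1. **Imaging contrasts.** Name days since last drink at the baseline scan as a covariate when AUD is compared with NAUD. For resting-state connectivity this means a linear model in place of the plain t-test in C4. For the permutation analyses it means one more design column. Fit it within the two alcohol groups only, because Table 1 sets no alcohol-free period for NUD and CS.
2. **Relapse.** The plan specifies no model for the NAUD-versus-AUD relapse prediction. State a regression of three-month relapse on group with days since last drink as a covariate.
3. **Reporting.** Show both sets of results with and without the covariate, and say in advance which one leads.
4. **Derivation.** Use the screening item plus days elapsed to the scan, checked against the Timeline Followback and the journals.
5. **Classifier.** Adding the variable as an SA2b feature may help prediction. It should not be described as control of confounding.
6. **Clarification.** The sponsor should reconcile Table 1, the instrument wording in C1 and the phrase in C11 by stating when the look-back month ends, what abstinence period applies and on which date each is judged. No choice among them is proposed here.

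**Cost.** Amendment wording and no new data collection. Each linear contrast loses one degree of freedom. The standard error could rise by about 3% if the groups differ by 7 days and the correlation is only 0.1. There are two sets of results to report. The cost in the relapse regression cannot be sized, because the plan projects no relapse numbers.
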